1. SYNOPSIS

Study Title	Predicting individual response to analgesic treatment with lidocaine in painful diabetic peripheral neuropathy (DPN)
Objective	To test, in a prospective, randomized, double-blind, placebo-controlled study, whether quantitative sensory measures predict the response to treatment with systemic sodium channel blocker lidocaine in patients with painful DPN.
Hypothesis	Among patients with painful DPN, those with higher mechanical pain threshold (MPT) or heat pain threshold (HPT) are more likely to respond to analgesic treatment with intravenous lidocaine.
Study Period	Planned enrollment duration: Approximately 24 months Planned study duration: 3 days per subject (1 enrollment and 2 treatment visits), with 3 week washout between the last 2 visits.
Number of Patients	35 evaluable patients with painful DPN completing the study
Study Treatment	Single intravenous 40-min infusion with 5mg/kg lidocaine or normal saline (placebo).
Study Design	Prospective, randomized, double-blind, placebo-controlled, cross-over study.
Inclusion and Exclusion Criteria	
Inclusion criteria:
 
 1. Age ≥ 18; 2. Diagnosis of Diabetes Mellitus (Fasting Plasma Glucose > 126 mg/dL and/or HbA1C $> 6.5\%$); 3. Distal symmetric pain in lower extremities with duration of more than 3 months; 4. Presence of either numbness or at least 1 sensory disturbance (increased or decreased sensitivity) in the feet. 5. Spontaneous pain with intensity of ≥ 4 on 0-10 Numerical Rating Scale (NRS). 
Exclusion criteria:
 
 1. Not giving consent to participate in the study; 2. Unable to complete self-report pain questionnaire; 3. History of moderate to severe renal or liver failure; 4. History of other central or peripheral neurologic disorders; 5. History of cardiac arrhythmias; 6. Contraindication to intravenous lidocaine; 7. Pregnancy or lactation.
Measurements	
Baseline sensory testing:
 
 1. Quantitative sensory testing (QST): Thermal detection and pain thresholds, mechanical detection and pain thresholds, pressure pain thresholds, temporal summation presence, and conditioned pain modulation (CPM). 2. Spontaneous pain at baseline on 0-10 Numerical Rating Scale (NRS); 3. Assessment of pain symptoms on Neuropathic Pain Symptom Inventory (NPSI) and Brief Pain Inventory (BPI).

	
Testing for intervention response (repetitive testing):
 
 1. Spontaneous pain intensity on 0-10 NRS and 0-100 computerized visual analog scale (CoVAS); 2. Response to warm, cold, pinprick and brush stimuli on 0-10 scale (0 -not felt, 5 – normal, 10 - most intensely felt); 3. Pain descriptors on NPSI questionnaire (burning, squeezing, pins and needles, tingling, stabbing, electrical shocks) on 0-10 scale; 4. Measurement of nociception level (NoL) index with finger probe (PMD 100 device); 5. Lidocaine plasma concentrations.

Statistical Methodology
	
The comparison between the analgesic effectiveness associated with each putative predictor of response (MPT and HPT) to lidocaine and to placebo will be performed by the following method: We will perform t-test in a multiple linear regression model to test the difference between slopes of predictor magnitude vs. response magnitude, namely: 1) Compare the slopes of MPT magnitude vs. lidocaine response magnitude (% reduction in pain intensity) curve, and MPT magnitude vs. placebo response magnitude (% reduction in pain intensity) curve. The same procedure will be performed for HPT predictor. The time point for primary effectiveness (pain reduction) outcome is the average of pain intensity measured at 40, 50 and 60 min after beginning of the infusion.

2. STUDY PROTOCOL

2.1 Background and Significance

Diabetic peripheral neuropathy (DPN) is a neuropathic pain condition, where the pain is caused by the metabolic damage to the somatosensory nervous system, and is in fact, the leading cause of neuropathic pain worldwide. It is estimated that more than 3 million Americans suffer from DPN [1], and with projected rise in the prevalence of diabetes mellitus (DM), this number is expected to increase. The metabolic consequences of DM lead to functional and structural damage of the peripheral nerve fibers [2, 3] and long-term changes within neuronal cell bodies in the dorsal root ganglia (DRG) and in the central nervous system (spinal cord and brain). The clinical translation of the structural and functional neuronal changes in DM is yet to be fully understood, but assumed to include the characteristic features of DPN – e.g. mixed areas of increased and decreased skin sensitivity, spontaneous ongoing pain, enhanced responses to painful stimuli, and pain produced by non-painful thermal and mechanical stimuli such as cold temperatures or light touch [4-6]. The clinical effectiveness of currently available drugs to treat DPN (e.g. gabapentin, pregabalin, duloxetine) is far from satisfactory, providing significant pain relief in approximately one of every 4-5 patients [7]. However, while some DPN patients don't respond to certain treatments, others respond very well. This suggests that variability exist among the underlying pain mechanisms on the patient level, and also points to individual differences in response to analgesics. Recent literature suggests that certain methods of assessing sensory nerve function in neuropathic pain patients may provide prediction to individual analgesic response [8-10]; however, no placebo-controlled studies have been performed with the primary goal of identifying treatment response predictors in DPN (or any other neuropathic pain condition).

This approach of identifying and validating predictors of individual response to a pharmacological treatment may substantially improve treatment outcomes in diabetic patients suffering from neuropathic pain. Applying a set of sensory tests that would provide information on the likelihood of effectiveness of a specific treatment can have a significant clinically-relevant impact in reducing unnecessary side effects, burden and costs associated with “trial and error” attempts to identify efficacious individual therapy option in DPN.

One of the key mechanisms that lead to spontaneous and evoked pain characteristic in DPN is alteration in the expression of voltage-gated sodium channels both peripherally and centrally [6, 11, 12], and these channels present a pharmacological target for many of the currently used drugs (e.g. carbamazepine, oxcarbazepine, lamotrigine, amitriptyline, and mexiletine). In our recent study, we found that patients with distal symmetric polyneuropathy (primarily due to DPN) respond to systemic administration of a sodium channel blocker lidocaine better than patients with other types of neuropathic pain [13]. Moreover, certain baseline somatosensory characteristics, namely – mechanical pain threshold (MPT) and heat pain threshold (HPT) were correlated with the extent of response to lidocaine [14]. These preliminary data led us to design this prospective, double blind, placebo-controlled study with the primary objective of determining whether these somatosensory parameters predict the response to systemic lidocaine in patients with painful DPN.

Intravenous lidocaine administration is approved by the FDA for the treatment of cardiac arrhythmias, for infusion in concentrations between 4-8mg/mL.

2.2 Preliminary Data

We have previously carried out a prospective study of intravenous lidocaine in two patient populations with peripheral neuropathic pain: 1. Patients after surgical or traumatic peripheral nerve injury, 2. Patients with distal symmetric polyneuropathy such as DPN.

The study was carried out with the same administration protocol of lidocaine (5mg/kg), and has utilized a similar sensory testing protocol.

[figure not shown]

Figure 1. Intravenous lidocaine infusion resulted in significantly larger reduction in spontaneous pain intensity in polyneuropathy patients (white circles) than in peripheral nerve injury patients (black circles). White triangles represent the average group response at each point.

Patients with symmetric polyneuropathy had better analgesic response to intravenous lidocaine infusion than patients with neuropathic pain due to nerve injury (Fig. 1).

Among different sensory measures tested, the two most significant predictors of treatment response to lidocaine (in polyneuropathy patients) were MPT and HTP (Fig. 2)

The patients reported only mild adverse effects during the infusion, and no patients required treatment for adverse effects. In 6 of 14 patients the infusion was briefly paused (for 5-13 minutes) because of transient dizziness (5 patients) or blurred vision (1 patient).

This study was not placebo controlled; therefore, it is unclear whether the identified predictors of response are specific to lidocaine.

[figure not shown]

Figure 2. Spontaneous pain reduction correlated with Mechanical Pain Threshold (MPT, Panel A), and Heat Pain Threshold (HPT, Panel B).

2.3 Objective

The objective of the proposed study is to test whether quantitative sensory measures predict the response to treatment with systemic sodium channel blocker lidocaine in patients with painful DPN.

The specific aims of this study are:

1. To investigate whether the baseline mechanical pain threshold (MPT) predicts the individual response to intravenous lidocaine treatment in DPN.
2. To investigate whether the baseline heat pain threshold (HPT) predicts the individual response to intravenous lidocaine treatment in DPN.

2.4 Patient Selection

Thirty-five evaluable patients with painful DPN will be recruited from the Diabetes Center and the Pain Management Center of Washington University in St. Louis.

2.4.1 Inclusion Criteria

Inclusion criteria:

1. Age ≥ 18 ;
2. Diagnosis of Diabetes Mellitus (Fasting Plasma Glucose > 126 mg/dL and/or HbA1C $> 6.5\%$);
3. Distal symmetric pain in lower extremities with duration of more than 3 months;

4. Presence of either numbness or at least 1 sensory disturbance (increased or decreased sensitivity) in the feet.
5. Spontaneous pain with average (past week) intensity of ≥ 4 on 0-10 Numerical Rating Scale (NRS).

2.4.2 Exclusion Criteria

Subjects will not be enrolled if any of the following criteria exist:

1. Not giving consent to participate in the study;
2. Unable to complete self-report pain questionnaire;
3. History of moderate to severe renal or liver failure;
4. History of other central or peripheral neurologic disorders;
5. History of cardiac arrhythmias;
6. Contraindication to intravenous lidocaine;
7. Pregnancy or lactation.

2.5 Design and Procedures

2.5.1 Study Design

This is a prospective, randomized, double-blind, placebo-controlled, cross-over study in 35 patients with painful DPN. If our hypothesis is confirmed, then patients with higher MPT or HPT at baseline will have larger analgesic effect from lidocaine infusion.

Randomization and Blinding

Eligible patients will attend a screening visit and two intervention visits, during which intravenous lidocaine or placebo infusion will be administered in a cross-over design. At enrollment, each patient will be assigned a study number, which will match a previously prepared computer-generated list of randomization numbers to determine the sequence of interventions: lidocaine and then placebo, or *vice versa*. An unblinded investigator will be assigned to match the study number with randomized treatment sequence, and this person will prepare the study medications, which will look identical. This investigator will not be involved at any stage at patient assessment or data analysis. The participants and all other study personnel will be blinded to the treatment allocation.

Sample size

In order to identify significant differences in slopes of predictor of response magnitude vs pain reduction curve in lidocaine group and placebo group, 34 patients will be required for this cross-over trial. The calculation is based on the ability to detect difference of 14 (SD 18.21) units between correlation coefficients of the two curves, based on our pilot data [14] (the calculation was performed for 85% power, and $\alpha = 0.025$, after Bonferroni correction for two comparisons; MPT and HPT). The enrollment will continue until 35 participants have completed both phases of treatment.

2.5.2 Pre-Study Period

Potential subjects will be identified from the Pain Management Center and the Diabetes Center of Washington University in St Louis. Patients will be asked by their attending physician in the clinics for approval to provide their name and contact information to the research team. In addition, we will post flyers and recruit participants through Volunteers for Health organization. Interested subjects will contact the investigators. Once the potential subject has contacted a member of the research team, a research coordinator will provide a description of the project either by phone, email or mail, at the discretion of the potential subject. Potential subjects will be asked to undergo telephone screening by a trained research coordinator to assess preliminary eligibility for the study.

The following information will be collected:

- Age;
- History of Diabetes Mellitus;
- Presence of pain in the extremities;
- Duration of pain
- Average intensity of pain
- Presence of numbness in the feet and any changes in sensation
- History of kidney or liver failure
- Allergies to lidocaine.
- Pregnancy or lactation

Eligible patients will be invited to participate in the study, which will be conducted at Washington University Pain Management Center.

Subjects who are potential candidates for the study will be provided with written and oral description of the study procedures, benefits, and potential risks. They will be given the opportunity to ask questions regarding the study. Informed consent will take place at Washington University/Barnes-Jewish Hospital medical center campus, including the Pain and Diabetes Centers.

If agreeing to participate in the study, each subject will sign informed consent form.

Each subject who qualifies for entry into the study on the basis of inclusion/exclusion criteria and completion of informed consent will be assigned the next available patient number. This indicates enrollment in the study. In subjects with a history of or suspected renal or hepatic disorder, blood tests will be ordered for plasma creatinine, Alanine aminotransferase (ALT), Aspartate aminotransferase (AST) and serum albumin. Subject with history of cardiac disease will be examined by 12-lead ECG to exclude active arrhythmias. Subjects with moderate or severe renal or hepatic failure, and subjects with active arrhythmias, will be excluded from the study at the discretion of the PI.

Patients' demographic data will be recorded; height and weight will be measured. The subject will be asked to complete the Brief Pain Inventory (BPI) AND Hospital Anxiety and Depression Scale (HADS). Subjects who drop out of the study prior to completing the study will be replaced by using the next available patient number.

2.5.3 Study Period

Subjects will be studied in the Washington University Pain Management Center. Eligible subjects will attend two treatment visits, during which intravenous lidocaine or placebo infusion will be administered in randomized order in double-blinded fashion. Subjects are instructed to refrain from eating 4 hours prior to the lidocaine infusion, but can drink clear liquids up to 2 hours prior to the procedure. The infusion start will be planned approximately at 10am; therefore subjects will be allowed to have a light snack before 6am if required for taking their DM medications (e.g. metformin). At each of these visits the subjects will undergo a quantitative sensory testing procedure to determine the MPT and HPT parameters [15]. MPT will be measured using a standardized weighted metal probes (Nervetest, MRC systems) using a modified method of levels, and HPT will be measured with Thermal Sensory Analyzer (TSA-II, Medoc, Israel) using the method of limits. In addition, other quantitative sensory measures will be obtained to better characterize the underlying nerve damage and possible pain mechanism. Namely, we will assess mechanical detection threshold (MDT) with von Frey filaments, cold and warm detection thresholds (CDT and WDT), as well as cold pain threshold (CPT) with TSA-II device, per previously published standard protocol [13, 15]. We will also apply conditioned pain modulation (CPM) protocol to assess the efficiency of descending inhibitory pain controls, as this was suggested to predict response to treatment in DPN [10], and lidocaine was shown to affect the descending inhibitory controls [16]. CPM protocol will tests whether concomitant application (conditioning) of a mildly painful stimulus on an upper extremity

(heat that elicits individually calibrated pain intensity of 30 on 0-100 NRS) reduces the painful experience from a painful (test) stimulus applied to the contralateral extremity (a thermal stimulus at temperature previously calibrated to elicit pain with intensity of 60 on 0-100 NRS). Reduction of reported pain experience to test stimulus during conditioning is a surrogate measure of efficient descending pain modulation.

At each of the intervention visits, an intravenous catheter will be inserted in the arm for drug administration, and in the opposite arm for obtaining blood samples to evaluate the plasma concentrations of lidocaine. The dose of lidocaine will be 5mg/kg ideal body weight (IBW), calculated by B. J. Devine Formula:

$$IBW = 50.0 + 2.3 \text{ kg per inch over 5 feet} \quad (\text{man})$$

$$IBW = 45.5 + 2.3 \text{ kg per inch over 5 feet} \quad (\text{woman})$$

Lidocaine will be infused during 40 minutes. The unblinded investigator will prepare 100mL normal saline infusion bags either with lidocaine or the same volume of normal saline (placebo). For lidocaine infusion, saline will be first drawn from the infusion bag in a volume equal to lidocaine volume to be added to the infusion, to keep the same total volume of the infusion bag. The total lidocaine dose will be limited to 500mg for safety reasons. The subjects will have continuous 3-lead ECG monitoring for 90 minutes.

Prior to infusion, we will assess:

1. Spontaneous pain intensity on 0-10 NRS.
2. NPSI pain descriptors burning, squeezing, pins and needles, tingling, stabbing, electrical shocks) on 0-10 scale
3. Evoked response (0-10 NRS) to cold (20°C, Rolltemp, Somedic), warm (40°C, Rolltemp, Somedic), brush (Senselab brush-05, Somedic) and pinprick (256mN metal probe, MRC Systems) stimuli applied to a dorsal foot and a non-painful control site (ipsilateral shoulder).

Tabular description of the study assessments is available in Table 1.

Table 1. Data assessment schedule

Required Assessments	Baseline visit	Treatment Visit 1	Washout			Treatment visit 2	Week 1b	Week 2b	Week 3b	End of Study communication
			Week 1a	Week 2a	Week 3a					
Informed consent	✓									
Inclusion/exclusion criteria	✓									
Randomization	✓									
Demographic data collection	✓									
BPI questionnaire	✓									
HADS questionnaire	✓									
Sensory Mapping	✓									
Assessment of sensitivity to cold, warm, brus and pinprick		✓				✓				
NoL measurement		✓				✓				
NPSI questionnaire		✓				✓				
QST		✓				✓				
CPM		✓				✓				
Blood sampling for PK		✓				✓				
Pain intensity 0-10 NRS		✓	daily	daily	daily	✓	daily	daily	daily	✓
Adverse Event assessment		✓				✓				✓
Blinding questionnaire										✓

With the beginning of the infusion, pain and the above mechanical and thermal evoked responses will be assessed every 10 minutes for 60 minutes, and then spontaneous pain will be assessed every 15 minutes for the next hour (total 120 min from the beginning of infusion). NPSI will be assessed at 60 min post-infusion.

In addition, skin temperature and blood flow will be assessed prior to and intermittently during the study drug infusion by an epidermal patch that rests on the skin surface. The thermal sensors, referred to as epidermal transient plane source (ETPS) sensors, utilize the well-established transient plane source method toward the identification of the thermal characteristics of skin. The ETPS sensor capabilities have been thoroughly studied [17], and the device concepts have been employed successfully in clinical studies related to blood flow [18], dermatological health [19], thermal transport properties of skin [20, 21], and wounds [22]. The measures that the ETPS sensors—cutaneous blood flow and temperature—are variables that have clear associations with inflammation and nociception, and can be used in this study as additional physiologic descriptors of the patient's disease and pain state.

Blood samples (4mL tubes) for determining lidocaine concentration will be obtained at baseline, and at 20, 45, 60, 90, and 120 minutes after beginning of the infusion. The samples will be put on ice, centrifuged for 10 min at 5000 rpm, plasma will be transferred to 1.5mL vials and stored at -80°C until analysis by HPLC-MS.

After discharge, average daily spontaneous pain intensity on 0-10 NRS will be recorded in a diary (q pm) for 3 weeks after each infusion. The infusions will be administered 3 weeks apart, as some studies have reported analgesic effect of a single lidocaine infusion lasting for up to 14 days.

ECG and oxygen saturation by pulse oximetry will be monitored throughout the infusion and for approx. 60 min after the end of infusion. Meals and oral fluids will be provided 1 hour after the end of lidocaine infusion. Subjects will be discharged from the unit after a minimum stay of 90 minutes after the end of infusion, and if no neurological or cardiac adverse effects are present, or when any such effects have completely resolved. In case of continuing adverse effects, the subjects will be monitored by the study staff until resolution of these effects as determined by the PI. At the end of the session the IV will be removed and subjects may go home. Subjects are not allowed to drive or operate machinery on the day of the study session.

Intravenous lidocaine infusion may cause dizziness and drowsiness; therefore, there is a risk of falling if the patient attempts to walk without assistance soon after the end of infusion. Subjects will be monitored to ensure they do not stand up or walk without assistance for up to 90 min after the end of infusion. The patients will be required to have a family member escort them home, and transportation will be provided if necessary.

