2.5.5 Observations and Measurements

2.5.5.1 Primary Outcome Measures

Primary outcome:

Reduction in spontaneous pain intensity on 0-10 NRS in the feet at 50 minutes after beginning the intravenous lidocaine infusion. This endpoint is calculated as the average of pain intensities measured at 40, 50 and 60 min after beginning of the infusion.

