2.5.7 Statistical Methods

The comparison between the analgesic effectiveness associated with each putative predictor of response (MPT and HPT) to lidocaine and to placebo will be performed by the following method: We will perform t-test in a multiple linear regression model to test the difference between slopes of predictor magnitude vs. response magnitude, namely: 1) Compare the slopes of MPT magnitude vs. lidocaine response magnitude (% reduction in pain intensity) curve, and MPT magnitude vs. placebo response magnitude (% reduction in pain intensity) curve. The same procedure will be performed for HPT predictor.

The time point for primary effectiveness (pain reduction) outcome is 50 min after beginning of the infusion, based on our preliminary data. This will be calculated from the average of pain intensities at 40, 50 and 60 min from the beginning of the infusion.

The time point for secondary outcome of change in NPSI pain descriptors is 45 min after beginning of the infusion.

In exploratory phase, multiple regression analysis will be performed to investigate how the combination of various sensory phenotypes assessed in this study (i.e. MPT, HPT, WDT, MDT, CDT, CPT, and CPM) and lidocaine pharmacokinetics (area under the concentration-time curve, (AUC) and maximal plasma concentration (Cmax)) correlate with treatment response to lidocaine.

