2.5.8 Sample Size

In order to identify significant differences in slopes of predictor of response magnitude vs pain reduction curve in lidocaine group and placebo group, 34 patients will be required for this cross-over trial. The calculation is based on the ability to detect difference of 14 (SD 18.21) units between correlation coefficients of the two curves, based on our pilot data [14] (the calculation was performed for 85% power, and $\alpha = 0.025$, after Bonferroni correction for two comparisons; MPT and HPT). The enrollment will continue until 35 participants have completed both phases of treatment.

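### The primary % reduction compares a mean of three post-infusion ratings with one listed pre-infusion rating and an unnamed denominator; averaging the pre-infusion rating too would be a cheap gain in precision

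*Combined protocol and SAP*

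**What the plan says.** Section 2.5.3 lists the assessments made before each infusion. The first is "Spontaneous pain intensity on 0-10 NRS", with no repeat and no averaging. After the infusion starts, "pain and the above mechanical and thermal evoked responses will be assessed every 10 minutes for 60 minutes". Table 1 has one tick for NRS at each treatment visit.

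Section 2.5.5.1 defines the primary outcome as "Reduction in spontaneous pain intensity on 0-10 NRS in the feet at 50 minutes after beginning the intravenous lidocaine infusion" and adds: "This endpoint is calculated as the average of pain intensities measured at 40, 50 and 60 min after beginning of the infusion". It does not say whether the reduction is absolute or relative. Section 2.5.7 and the synopsis use the relative form, as in "lidocaine response magnitude (% reduction in pain intensity) curve", and apply the same form to placebo. Neither names the denominator.

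The same-visit pre-infusion rating is the natural candidate. The entry criterion in section 2.4.1 ("Spontaneous pain with average (past week) intensity of" 4 or more) is an enrolment value. The daily diary in Table 1 starts only after the first infusion, so it gives no reference for treatment visit 1.

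On sensory testing, section 2.5.3 says: "At each of these visits the subjects will undergo a quantitative sensory testing procedure to determine the MPT and HPT parameters". It states neither the order of that testing and the pre-infusion rating nor any interval between them.

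**The concern.** The plan averages three readings to steady the post-infusion value, then divides by a pre-infusion value that is not averaged. Rating error in the reference enters the response at both visits, and so adds scatter around both slopes that the primary test compares. The error in a % reduction also scales with 1/baseline. Entry requires a past-week average of at least 4, but no minimum applies to the rating on the treatment day, so one low rating can produce an extreme % reduction among only 35 completers.

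What is at stake is precision. If rating error is unrelated to MPT and HPT and similar at both visits, it widens the standard error of each slope without favouring either treatment.

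**Working it through.** **The plan's own figure.** The documents give no figure for rating error. The nearest is the sample size in section 2.5.8, "34 patients will be required for this cross-over trial" (difference 14, SD 18.21, 85% power, alpha 0.025). Taking 18.21 as a per-treatment SD and alpha as one-sided, the normal approximation gives 2 × (18.21/14)² × (1.960 + 1.036)² = 30.4, so 31. The cross-over t calculation gives 33, with power 0.867 at 34. Two-sided, the t calculation gives 39. So 34 is approximately recovered only on the one-sided reading. The 18.21 is expressed in units of correlation coefficients, so it cannot be converted to a rating-error SD, and no revised N follows from what is below.

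**Inputs.** From the documents: one pre-infusion rating, three post-infusion readings, % scale. Assumed, because the documents are silent: SD *s* of one rating, equal before and after; error correlation ρ within a set of readings, none between the pre and post sets; pre-infusion pain *B* of 4 to 8; the size of the true reduction.

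**Formula.** With R = 100 × (1 − post/pre) and q = post/pre = 1 − true reduction, the delta method gives

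Var(R) = (100/B)² × s² × [q² × c + (1 + 2ρ)/3],

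where c = 1 for one pre-infusion rating and c = (1 + 2ρ)/3 for the mean of three. With one rating, the pre-infusion share is q² / [q² + (1 + 2ρ)/3].

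**At a 30% reduction (q² = 0.49).**
- ρ = 0, one rating: 0.49 + 0.333 = 0.823; share 0.49/0.823 = 60%.
- ρ = 0, three ratings: 0.163 + 0.333 = 0.497; variance cut 1 − 0.497/0.823 = 40%, or 22% in SD.
- ρ = 0.5, one rating: 0.49 + 0.667 = 1.157; share 42%.
- ρ = 0.5, three ratings: 0.327 + 0.667 = 0.993; variance cut 14%.

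**Other reductions.**

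| True reduction | Pre-rating share, ρ = 0 | Variance cut, ρ = 0 | Pre-rating share, ρ = 0.5 | Variance cut, ρ = 0.5 |
|---|---|---|---|---|
| 0% | 75% | 50% | 60% | 20% |
| 20% | 66% | 44% | 49% | 16% |
| 30% | 60% | 40% | 42% | 14% |
| 50% | 43% | 29% | 27% | 9% |
| 70% | 21% | 14% | 12% | 4% |

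**Crossover.** The two sources are equal when q² = (1 + 2ρ)/3. For ρ = 0, q = 0.577, a reduction of 42.3%. For ρ = 0.3 it is 27%, for ρ = 0.5 it is 18%, and for ρ = 0.8 it is 7%.

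**In points of % reduction (ρ = 0, 30% reduction).** With s = 0.8, the rating-error SD falls from 12.1 to 9.4 at B = 6 and from 18.1 to 14.1 at B = 4.

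**Check on the bounded 0-10 scale.** Simulation with independent errors, B from 4 to 8 and s from 0.5 to 1, gave pre-rating shares of 76-86% at no reduction, 60-75% at 30%, 44-61% at 50% and 22-40% at 70%. The delta method therefore understates the share somewhat when baseline pain is low and ratings are noisy, but the pattern is the same.

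**If the outcome were absolute reduction,** the share would be 1/(1 + 1/3) = 75% at every size of reduction (ρ = 0). This is one reason to settle the scale in section 2.5.5.1.

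**The case against.** A reader might infer that the single rating dominates the error of every % reduction. It does not. Above about 42%, or above 18% with ρ = 0.5, the post-infusion readings are the larger source, and strong responders are the patients the predictor hypothesis is about. Readings 10 minutes apart in one session plausibly share error, so the independent case is the favourable end. This stands and limits the claim. It does not remove the gain, which is positive in every case tabulated.

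A reader might also infer that QST on the painful foot raises the pre-infusion rating and inflates the apparent response. The documents do not establish that. No order or interval is stated. Under section 2.5.6 the threshold tests end at first pain or at the stop button; only the wind-up trains have fixed force. Section 3.3.2 says thermal-test pain generally subsides at once. In narrative order, catheter placement falls between QST and the rating. The later readings are themselves taken amid a repeated evoked battery. A similar shift at both visits moves both intercepts and does not by itself change the slope difference. Residual pain could in principle track MPT or HPT, since stimulation continues until threshold, but its size is unknown and it would partly cancel between visits.

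Rating error is only part of the scatter. Suppose a total residual SD of 25 points (an assumption), s = 0.8, B = 6 and a 30% reduction. Independent errors give √(625 − 0.327 × 13.33²) = 23.8, about 5% lower; ρ = 0.5 gives √(625 − 0.163 × 13.33²) = 24.4, about 2% lower. At B = 4 with independent errors it is √(625 − 0.327 × 20²) = 22.2, about 11% lower. So the gain may be modest.

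Finally, the wording on readings from the start of the infusion does not clearly rule out a time-0 reading. That is fair, but the plan does not say that such a reading would enter the reference.

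**Conclusion.** The point holds as a precision improvement. The plan lists one pre-infusion rating against a mean of three and does not name the denominator of its primary response. Under independent, equal errors, the single rating is the larger source of rating error for reductions below about 42%, a range that probably covers many placebo responses, and the placebo slope is half of the primary contrast. With ρ = 0.5 the crossover is about 18%. At a 30% reduction, averaging three ratings would lower rating-error variance by about 40% to 14% across those two cases.

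These figures rest on the same-visit pre-infusion rating being the reference, and on assumed values for rating correlation and size of reduction. The effect on total residual variance, power or N cannot be derived from the documents. Nothing here shows bias in the slope comparison, and the trial remains interpretable without the change. The unnamed denominator needs settling whether or not the extra ratings are adopted.

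**What to change.** In section 2.5.3, record spontaneous foot NRS three times before each infusion, for example at 10-minute spacing, after QST and CPM are complete and before that visit's evoked stimuli. Use catheter and monitor set-up time where possible. In sections 2.5.5.1 and 2.5.7, define the reference for % reduction as the mean of these three ratings, identically at both visits, and state in 2.5.5.1 that the outcome is % reduction. If the extra ratings are not adopted, still name the single reference rating and fix its place relative to QST.

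Cost: two extra verbal ratings and up to about 20 minutes per visit, partly absorbed by set-up. Patients are fasting with a planned start near 10am, so the added wait should be fitted to that schedule. No extra patients or procedures are needed.
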